vaginal stents are routinely placed via a number of procedures which can vary enormously by indication. Some inpatient procedures require stays in hospital with a tractioned vaginal stent for up to 5 days. These patients then wear a stent intermittently thereafter for up to 4 weeks depending on vaginal healing. Outpatient procedures may require use of a vaginal stent intermittently for up to two weeks. Patients are currently required to be able to remove and reinsert the vaginal stent themselves at home (usually same stent that is washed and re-used). However, due to the relative non-existence of a commercially available product, physicians are relegated to creating their own makeshift stents for their gynecology patients either using finger slots from sterile gloves and gauze, sterile cement coated in bone wax and placed in a condom, or plastic moulding. All of these are suboptimal options with resultant low patient compliance, stent egress and emergency room hospital visits for replacements, and poor patient outcomes.

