3b: Demonstrate that retention of our novel vaginal stent in the vaginal canal is superior to that of existing makeshift / handmade vaginal stents.

By leveraging the unique medical database available at our institutions (Texas Children's Hospital and Baylor College of Medicine), we will demonstrate success of our new vaginal stent by comparing the number of vaginal stents still in place at a 2-week post-surgical follow-up in neovaginal surgery.

Section E: Protocol Risks/Subjects

E1. Risk Category

Category 2: Research involving greater than minimal risk, but presenting the prospect of direct benefit to the individual subjects.

E2. Subjects

Gender:

Female

Age:

Adolescent (13-17 yrs), Adult (18-64 yrs)

Ethnicity:

All Ethnicities

Primary Language:

English, Spanish

Groups to be recruited will include:

Both patients and healthy, non-patient, normals

Which if any of the following vulnerable populations will be recruited as subjects?

Children

Vulnerable populations require special protections. How will you obtain informed consent, protect subject confidentiality, and prevent undue coercion?

Informed consent will be obtained by trained research personnel. An initial screening interview via phone will be held, followed by an invitation to speak with a study coordinator (plus interpreter if needed). The study risks and procedures will be fully explained, eligibility assessed, and the participants' rights enumerated (including the right to withdraw at any time). Potential participants will be given time to answer questions. For subjects under age 18, parental consent and adolescent assent will be obtained prior to participation. Subject confidentiality will be maintained at all times; phone calls and in-person recruitment will be held in private rooms. All patient information will be kept on a secure, HIPAA-compliant electronic server or in a locked file cabinet when not in use.

Please note The Spanish forms -consent form, recruitment flyers, questionnaires- are being translated as of 2/2/21.

We will attach these forms when translation is complete.

E3. Pregnant woman/fetus

Will pregnant women and/or fetuses (as described in 45 CFR 46 Subpart B) be enrolled in the research?

No

E4. Neonates

Will neonates of uncertain viability or nonviable neonates (as described in 45 CFR 46 Subpart B) be enrolled in the research?

No

E5. Children

Will children be enrolled in the research?

Yes

Section F: Design/Procedure

F1. Design

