a) Post-Surgical Adolescent Patients: Subjects will complete Pre-Stent Questionnaire. Prior to surgery, patients will undergo standard of care (SOC) testing including urine pregnancy and infection screening. The vaginal canal and mucosa will be assessed while in the operating room by vaginoscopy and a vaginal culture collected to rule out preoperative infection and vaginal length measurement. Vaginal surgery will be carried out per indication. A sterilized, vaginal stent will be placed postoperatively in the operating room, and instructions given to patients prior to discharge. Patients will continue to wear the vaginal stent for two weeks without removal and complete daily questionnaire on retention and comfort.

At 2 weeks post-surgery, patients will complete evaluation of the stent including tolerability, ease of use, comfort, reasons for early discontinuation, as well as any vaginal symptoms such as pain, bleeding or other AE. They will then be reassessed in the operating room (SOC) for stent removal, vaginal length measurement, vaginal culture, urinalysis, evaluation of the vaginal mucosa via vaginoscopy to assess for adhesions, granulation tissue, stricture, and remaining septal tissue. Physicians will complete the VAF.

Subsequent Visits: Patient participants will be re-evaluated at 4 and 6 weeks and 3, 6, and 12 months postop in the clinic. This visit frequency is considered SOC for adolescents who are postop from vaginal reconstructive surgery. Measured outcomes will include possible pain, bleeding, painful intercourse at 3 months postop, difficulty with tampon insertion, menstrual fluid retention, need for vaginal dilators. A physical exam will also be completed including a single digit vaginal exam to evaluate stricture, granulation tissue and adhesions. Patients may also be asked to demonstrate

placement of the vaginal stent (used as a corollary to adequate and maintained vaginal caliber).

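### Aim 3b compares stents in place at the 2-week visit, but the new and handmade stents are worn under different regimens, so the measure mixes device with regimen and its net bias cannot be sized

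*Combined protocol and SAP*

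**What the plan says.** Section D, Specific Aim 3b, sets a superiority objective: "Demonstrate that retention of our novel vaginal stent in the vaginal canal is superior to that of existing makeshift / handmade vaginal stents". The comparator comes from existing records ("By leveraging the unique medical database available at our institutions"), and the measure is obtained by "comparing the number of vaginal stents still in place at a 2-week post-surgical follow-up in neovaginal surgery".

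The new stent's post-surgical regimen is in Section F2, Phase 3, group a: "Patients will continue to wear the vaginal stent for two weeks without removal". It is then removed in the operating room at the 2-week reassessment.

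Current handmade-stent care is described in Section C:

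- Inpatient procedures: "Some inpatient procedures require stays in hospital with a tractioned vaginal stent for up to 5 days", after which "These patients then wear a stent intermittently thereafter for up to 4 weeks depending on vaginal healing".
- Outpatient procedures: "Outpatient procedures may require use of a vaginal stent intermittently for up to two weeks".
- Handling at home: "Patients are currently required to be able to remove and reinsert the vaginal stent themselves at home".

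Section C also reports that handmade stents fall out and lead to emergency visits for replacement, without giving a rate. No section says how a handmade stent is coded if it is out by instruction, if its prescribed use has ended, or if it fell out and was put back.

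**The concern.** The same observation at the 2-week visit means different things in the two groups. For the new stent, absence means that it came out or was stopped early, because no removal is prescribed before the visit. For a handmade stent, absence can also mean that the patient is between periods of intermittent wear, or has finished the prescribed use. Presence is ambiguous too: a handmade stent seen at the visit may have fallen out earlier and been reinserted or replaced.

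Aim 3b could therefore report superiority when the two devices are equally prone to fall out, or miss a real advantage. Adding a statistical test to Section G2 would not help, because the difference in meaning lies in the endpoint.

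**Working it through.** The plan states no effect size, comparator rate or comparator number for Aim 3b, so there is no figure to reproduce. The check starts by setting the two regimens side by side.

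| State at the 2-week visit | New stent (F2, group a) | Handmade stent (Section C) |
|---|---|---|
| Out by instruction | Not prescribed before the visit | Possible under intermittent wear |
| Out because use is complete | Not before the visit | Possible after outpatient procedures |
| Out after egress | Not retained | Not retained |
| Out after early voluntary stop | Not retained | Not retained |
| In place after egress and reinsertion or replacement | Coding not stated | Literally retained |

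The first two rows lower the handmade count, and the last row raises it.

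**Illustration of size.** Every rate here is an assumption. Let *p* be the true proportion free of egress, the same for both devices, with *p* = 0.80. Let *s* be the share of handmade stents out at the visit by instruction or completed use. Let *r* be the share of handmade stents that fell out and were put back or replaced. Assume *s* applies equally whether or not a stent had fallen out, that a new stent that fell out counts as not retained, and that nobody stops early.

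- New stent in place = *p* = 0.80.
- Handmade stent in place = [*p* + (1 − *p*) × *r*] × (1 − *s*).

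The bracket is 0.80 for *r* = 0; 0.80 + 0.20 × 0.5 = 0.90 for *r* = 0.5; and 1.00 for *r* = 1. Each cell gives the handmade percentage in place, with the new-minus-handmade difference in points in parentheses.

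| *s* | *r* = 0 | *r* = 0.5 | *r* = 1 |
|---|---|---|---|
| 10% | 72 (+8) | 81 (−1) | 90 (−10) |
| 30% | 56 (+24) | 63 (+17) | 70 (+10) |
| 50% | 40 (+40) | 45 (+35) | 50 (+30) |

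The two routes cancel when *s* = 1 − 0.80 / bracket: 1 − 0.80/0.90 = 11% for *r* = 0.5, and 1 − 0.80/1.00 = 20% for *r* = 1. Below those shares the literal measure works against the new stent; above them it works for it.

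**Effect on a test, on the side that favours the new stent (*r* = 0).** The plan names no test for this comparison, so I assume a two-sided Fisher exact test at 0.05. The new-stent group has 10 patients, as in Section F1 (Section F2 gives 20 adolescents in one place). The table gives the exact probability of declaring the new stent better when both devices truly have 80%.

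| *s* | Comparator n = 10 | n = 30 | n = 50 |
|---|---|---|---|
| 0% | 0.4% | 0.7% | 0.3% |
| 25% (80% v 60%) | 5.8% | 13.8% | 16.2% |
| 50% (80% v 40%) | 25.3% | 50.0% | 60.6% |

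In these scenarios a larger chart sample does not cure the problem; with *s* above zero it makes a spurious finding more likely.

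**The case against.** The best reply is that the documents give no coding rule, so the aim is under-specified rather than shown to be mis-scored. Its heading speaks of retention, and Aim 3a ties efficacy to absence of egress and to compliance, so chart abstractors might code instructed removal sensibly. That is possible, but the only stated measure is presence at the visit, and nothing excludes instructed removal or completed use.

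Several limits do stand:

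- A reader might infer that the handmade stent fails whenever its instructions are followed. The documents do not support that. A patient on intermittent wear may be wearing the stent at the visit, inpatient wear can run past it, and Section C does not say which regimen neovaginal surgery uses.
- A reader might infer that the bias certainly favours the new stent. Reinsertion and replacement work the other way, so the net direction is not established.
- Absence of the new stent does not mean egress alone. Section F2 collects reasons for early discontinuation.
- Switching to unplanned egress alone would be incomplete. An intermittently worn stent can fall out only while inserted, and Aim 3a makes compliance part of efficacy.

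It is also fair to say that this is a feasibility study (Section G1), that no control cohort is recruited (Section F1), and that Section G2 contains no comparison with handmade stents. Those are separate gaps. Aim 3b remains a stated superiority objective, and filling them would leave the endpoint as it is.

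**Conclusion.** The point holds in this form: taken literally, the Aim 3b measure confounds device with wear regimen, because continuous wear is prescribed for the new stent and intermittent wear is described for the comparator. This rests on the wording of Sections C, D and F2, not on a calculation.

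Two opposing errors are built in, and the documents do not give the quantities needed to net them. Under the assumed 80% freedom from egress, the apparent difference between equally retained devices ranges from −10 to +40 points over the shares tried. Those figures show that the sign and size depend on unknown inputs; they do not estimate the bias. The change should be made before any chart comparison is carried out.

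**What to change.** In Aim 3b, and in the chart-abstraction form:

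1. Define failure in both groups as unplanned egress, including egress followed by reinsertion or replacement, or unscheduled early discontinuation, during the prescribed wear period and up to 2 weeks.
2. State that instructed removal and completed use are not failures.
3. Record and report the prescribed wear regimen for both groups.
4. Because time at risk differs between continuous and intermittent wear, state the conclusion as a comparison of device plus regimen, unless comparator charts with continuous wear exist and are used.

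The cost is a rewording of the aim and different abstraction fields; no patient's wear schedule changes. There is a downside. Egress and discontinuation handled at home are under-recorded in charts, and shorter time at risk under intermittent wear may make the comparator look better. Both make superiority harder to show and should be acknowledged in the report.

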a) Post-Surgical Adolescent Patients: Subjects will complete Pre-Stent Questionnaire. Prior to surgery, patients will undergo standard of care (SOC) testing including urine pregnancy and infection screening. The vaginal canal and mucosa will be assessed while in the operating room by vaginoscopy and a vaginal culture collected to rule out preoperative infection and vaginal length measurement. Vaginal surgery will be carried out per indication. A sterilized, vaginal stent will be placed postoperatively in the operating room, and instructions given to patients prior to discharge. Patients will continue to wear the vaginal stent for two weeks without removal and complete daily questionnaire on retention and comfort.

At 2 weeks post-surgery, patients will complete evaluation of the stent including tolerability, ease of use, comfort, reasons for early discontinuation, as well as any vaginal symptoms such as pain, bleeding or other AE. They will then be reassessed in the operating room (SOC) for stent removal, vaginal length measurement, vaginal culture, urinalysis, evaluation of the vaginal mucosa via vaginoscopy to assess for adhesions, granulation tissue, stricture, and remaining septal tissue. Physicians will complete the VAF.

Subsequent Visits: Patient participants will be re-evaluated at 4 and 6 weeks and 3, 6, and 12 months postop in the clinic. This visit frequency is considered SOC for adolescents who are postop from vaginal reconstructive surgery. Measured outcomes will include possible pain, bleeding, painful intercourse at 3 months postop, difficulty with tampon insertion, menstrual fluid retention, need for vaginal dilators. A physical exam will also be completed including a single digit vaginal exam to evaluate stricture, granulation tissue and adhesions. Patients may also be asked to demonstrate

placement of the vaginal stent (used as a corollary to adequate and maintained vaginal caliber).

b) Adult Females, Post-Radiation: Post-radiation vaginal fibrosis occurs more slowly than post-surgical fibrosis and these women do not have post-surgical wounds, so we expect the adult post-radiation patient population to be able to wear the vaginal stent continuously for two weeks and then for an additional 2 weeks. Following consent adult patients undergoing vaginal brachytherapy treatments, will complete Pre-Stent Questionnaire and the vaginal stent will be placed by [name] or another co-investigator physician at the conclusion of their final brachytherapy treatment. Prior to stent placement, the vaginal canal and mucosa will be assessed by speculum exam, vaginal culture, urine pregnancy test, and urinalysis will be obtained and the physician will complete the VAF. Instructions will be given to the patients prior to discharge. If the participant is at a high risk for tissue erosion, per physician discretion, she will be prescribed a topical vaginal estrogen (e.g. Premarin cream or Repagyn hyaluronic acid gel). It is SOC to prescribe vaginal estrogen to current patients with vaginal stents or pessaries who are at higher risk for tissue erosion (e.g. post-menopausal patients); thus, use of the cream or gel in the current study is not experimental. Participants will be sent a secure link to complete a daily questionnaire on retention and comfort.

Evaluation at 2 and 4 weeks: Patients will be examined in clinic by a physician co-investigator at 2 weeks post-stent placement. At the time of assessment, patients will complete evaluation surveys on the vaginal stent as well vaginal symptoms such as pain or bleeding. The vaginal stent will be removed and the vaginal cavity will be assessed by a physician for any adhesions, granulation tissue, stricture, fibrosis, necrosis by speculum exam and vaginal culture. Vaginal length will be measured. Physicians will also rate ease of stent removal and complete VAF for each patient. Any patient-reported symptoms will be documented. At 2 weeks, if no AEs are reported, vaginal stent will be replaced by a physician for an additional two weeks of use. If AEs are reported, clinical decisions regarding continued use of stent will be made. Participants will be sent a secure link to complete a daily survey. If no AE seen in first three patients, clinician may determine two week follow up is not necessary and patients can wear stent for four weeks continuously.

Subsequent Visits: Adult patients will be re-evaluated 3, 6, and 12 months as SOC. Patients will complete questionnaires regarding vaginal symptoms at each clinical visit as described above for adolescents. Physicians will complete the VAF regarding ease of instruction, placement, improvement over standard of care, overall utility for the stent system, and any complications. Outcomes will include pain, bleeding, painful intercourse at 3 months postop, difficulty with tampon insertion, menstrual fluid retention, and need for vaginal dilators. A physical exam will also be completed including a single digit vaginal exam to evaluate stricture, granulation tissue and adhesions. Patients may be asked to demonstrate placement of the vaginal stent (used as a corollary to adequate and maintained vaginal caliber).

AE monitoring: Participants will be informed about the potential for AEs at the screening call, first clinic visit, and at the visit for insertion of subsequent stents. Participants will be asked to report all AEs via a study phone line. A Data Safety Monitoring Board consisting of an independent investigator recruited from BCM clinical faculty will take responsibility for ensuring that all AEs are reported to the IRB at BCM, in accordance with their standard procedures. In the event of a severe AE (infection, bleeding, mucosal reaction, or inability to carry out Activities of Daily Living), the Board member and representatives from the BCM IRB will meet and discuss mitigation plans and plans for the study future. We anticipate that stopping criteria will include severe AEs in 20% of subjects. Data Safety Monitoring Plan is attached to Section S. Materials- Each vaginal stent system will be individually packaged. Healthy females will receive devices that are sanitary (akin to the cleanliness of a tampon) that have been swabbed with alcohol or other compatible solutions. Devices prepared for the patient population will undergo a 66-hour, costly sterilization process due to the vulnerability of the vaginal tissue after surgery and radiation treatment. The stent size most appropriate to the patients' age and approximate vaginal canal dimensions will be selected. Testing will be monitored by a physician at all stages of the project. All stents will be discarded after single use.

Participant feedback - Participants will be given questionnaires, via RedCap, with questions related to baseline vaginal metrics, stent comfort (during insertion, wear, removal), retention, ability to carry out normal Activities of Daily Living, and any AEs. At all points of instruction during clinic visits, patients will be given ample time to ask questions and voice concerns. A research coordinator or clinician will be available via phone for patient questions.

Section G: Sample Size/Data Analysis

G1. Sample Size

How many subjects (or specimens, or charts) will be used in this study?

Local: 40 Worldwide: 40

Please indicate why you chose the sample size proposed:

As a feasibility study, the low recruitment numbers will be used to evaluate the design concept with respect to functionality, comfort and any unforeseen safety issues (beyond those which were accounted for in earlier stages of the product design). The current participants will guide additional device refinements.

G2. Data Analysis

Provide a description of your plan for data analysis. State the types of comparisons you plan (e.g. comparison of means, comparison of proportions, regressions, analysis of variance). Which is the PRIMARY comparison/analysis? How will the analyses proposed relate to the primary purposes of your study?

Exploratory analyses of 20 healthy community participants: We code the stent as successful if, after 2 weeks, it has been retained in the vaginal canal. We will tentatively explore predictors of success using binomial logistic regression models, with a log-link estimator, which specify success (retained / not retained) as the outcome and participant group (under 18/over 18), and presence of bacterial / fungal infection at baseline and followup as three separate models. We will also run exploratory binomial logistic regression models, as above, with comfort, acceptability, ability to carry out normal Activities of Daily Living (ADLs), and number of AEs as outcomes, and participant group as the predictor. To maximize power, and recognize the exploratory nature of these analyses, we will not correct for multiple testing.

Analyses of 20 clinical patient participants: Initial analyses will compare the two patient groups on baseline characteristics (vaginal cavity assessments by physicians and patient and physician questionnaires) using two sample t-tests, specifying patient group as the predictor. T-tests were selected for the robust to non-normal distributions with small sample sizes, and their suitability to small sample sizes as low as four per group (ref: york.ac.uk/depts/math/histstat/student.pdf). Our main analyses will examine whether the stent was successful in our population (ie. examining whether the proportion of retained stents was significantly different from zero). A one-sample t-test will be run, with success (returned at 2 weeks coded as 1, not retained coded as 0) as the independent variable. Significance will be set at $P < .05$.

All analyses will be conducted in the latest version of R (version 5.1.2).

Section H: Potential Risks/Discomforts

H1. Potential Risks/Discomforts

Describe and assess any potential risks/discomforts; (physical, psychological, social, legal, or other) and assess the likelihood and seriousness of such risks:

The participant may experience mild discomfort while using the stent. A thorough vaginal assessment will be performed by a clinician immediately after insertion to assess for any discomfort outside of normal range.

The likelihood of adverse events is small but could include bleeding, displacement of the stent such as egress, urinary retention, mucosal irritation, tearing, erosion, abscess, granulation tissue, or infection. The principal investigator will likely stop the trial for persistent displacement (>5), tearing or erosion of tissue, or abscess. The principal investigator will likely pause the trial and assess for further detail in instances of urinary retention, mucosal irritation, granulation tissue, or infection.

More severe outcomes, however unlikely, include tearing of the mucosal lining, infection, irritation, urinary retention, bleeding, or formation of granulation tissue around the stent. The most severe outcomes include vaginal tearing and formation of a fistula (abnormal connection between two structures). Symptoms of a vaginal infection may include yellow/green vaginal discharge, vaginal pain, fevers, or abdominal pain. Symptoms of urinary retention may include inability to empty the bladder or pelvic pain. Symptoms of vaginal tearing or granulation tissue formation in the vagina may include unexpected vaginal bleeding or vaginal pain. Symptoms of a vaginal fistula may include passage of urine or feces from the vaginal cavity as well as fevers or pelvic and vaginal pain. These outcomes are highly unlikely and we do not expect them to occur. Please reference attachment "Adverse Event Grading Chart".

A clinician or study nurse will be available at all times via phone for additional participant questions or concerns.

H2. Data and safety monitoring plan

Do the study activities impart greater than minimal risk to subjects?

Yes

NOTE: The answer to the questions in H2 requires the completion of the form: 'Section H – Data and Safety Monitoring Plan' as an attachment in Section S.

H3. Coordination of information among sites for multi-site research

Is the BCM Principal Investigator acting as the SPONSOR-INVESTIGATOR for this multi-site research?

No or Not Applicable

Is BCM the COORDINATING CENTER for this multi-site research?

No or Not Applicable

Section I: Potential Benefits

Describe potential benefit(s) to be gained by the individual subject as a result of participating in the planned work.

There are no direct benefits from participating as a healthy volunteer. Clinical patients may benefit from a reduced likelihood of restenosis, additional surgeries, and scarring.

Describe potential benefit(s) to society of the planned work.

Benefits to society include improved post-surgical outcomes for females after pelvic surgery or radiation due to gynecologic cancer treatment. Increased comfort and effectiveness will increase adherence to wearing the stent, which will reduce the likelihood of restenosis, perineal dilation, surgical revision, and scarring. Sexual function is likely to improve. Overall, the improvements to quality of life will yield physical and psychological benefits for both patients and families, as well as significant health care cost savings.

Do anticipated benefits outweigh potential risks? Discuss the risk-to-benefit ratio.

Due to the unforeseen likelihood of experiencing an adverse event, compared to the potential to permanently improve the quality of life in young women after gynecologic revisions and gynecologic cancer populations, the anticipated benefits outweigh potential risks.

Section J: Consent Procedures

J1. Waiver of Consent

Will any portion of this research require a waiver of consent and authorization?

No

J1a. Waiver of requirement for written documentation of Consent

Will this research require a waiver of the requirement for written documentation of informed consent?

Yes

Explain how the research involves no more than minimal risk to the participants, and the specifics demonstrating that the research does not involve procedures for which written consent is normally required outside of the research context.

The waiver for written documentation of consent applies to physicians who will complete a vaginal assessment form. The form includes a cover letter (attached to Section S), indicating that completing any portion of the survey evidences their desire to participate in the study. Participating poses no more than minimal risk and will not affect their employment status in any way. Physician participant names will not be disclosed to anyone outside of the research team. Their responses will be kept confidential and reported only in aggregate, de-identified form.

J2. Consent Procedures

Who will recruit subjects for this study?

PI
PI's staff

Describe how research population will be identified, recruitment procedures, any waiting period between informing the prospective participant and obtaining consent, steps taken to minimize the possibility of coercion or undue influence and consent procedures in detail.

Potential participants will be recruited through flyers placed at hospitals, research institutions, and device accelerators within the Texas Medical Center, via the study recruitment pages of the BCM website, and through the electronic BCM and TCH newsletters. Flyers will also be sent to BCM graduate students, post docs, and medical students through list respective list servs. (See flyers in Section S.) Additional flyers may be placed on local college campuses. No individual will be allowed to participate that is or may be graded or trained by any co-investigator. Interested participants will be invited to speak to a study coordinator (plus an interpreter if needed). (However, no Spanish speaking individuals will be consented in the research until all applicable English documents - informed consent form, flyers, questionnaires- are translated into Spanish and submitted to the IRB via an amendment.) Interested participants will be provided a copy of the current informed consent document either via email or in the clinic prior to consenting in order to allow adequate time to review before the first appointment.

The meeting with the study coordinator will be held in a private room within the TCH Clinical Research Center or Pavilion for Women or Ben Taub Hospital. At that time, the study risks and procedures will be fully explained, eligibility assessed, and the participant's rights (including the right to withdraw at any time) enumerated. Eligibility will be determined by the inclusion and exclusion criteria described in Section F1. The study coordinator will review the criteria

with interested participants to determine eligibility. If eligible, the study coordinator will review the consent form and reiterate items related to study objectives, procedures, risks, benefits, compensation, and participant rights. Adequate time will be given for any questions the potential participant may have. The potential participant will have the option of signing the consent form at that time, declining participation, or returning at a later date to provide consent.

Are foreign language consent forms required for this protocol?

Yes

Which of the following ways will you document informed consent in languages other than English?

A full-length informed consent document

J3. Privacy and Intrusiveness

Will the research involve observation or intrusion in situations where the subjects would normally have an expectation of privacy?

No

J4. Children

Will children be enrolled in the research?

Yes

J5. Neonates

Will non-viable neonates or neonates of uncertain viability be involved in research?

No

J6. Consent Capacity - Adults who lack capacity

Will Adult subjects who lack the capacity to give informed consent be enrolled in the research?

No

J7. Prisoners

Will Prisoners be enrolled in the research?

No

Section K: Research Related Health Information and Confidentiality

Will research data include identifiable subject information?

Yes

Information from health records such as diagnoses, progress notes, medications, lab or radiology findings, etc.

Yes

Specific information concerning alcohol abuse:

No

Specific information concerning drug abuse:

No

Specific information concerning sickle cell anemia:

No

Specific information concerning HIV:

No

Specific information concerning psychiatry notes:

No

Demographic information (name, D.O.B., age, gender, race, etc.):

Yes

Full Social Security #:

Yes

Partial Social Security # (Last four digits):

No

Billing or financial records:

No

Photographs, videotapes, and/or audiotapes of you:

No

Identifiable biospecimens

No

Other:

No

At what institution will the physical research data be kept?

Records will be kept in a secure area at in locked credenzas or investigator offices at Texas Children's Hospital and Baylor College of Medicine. Minimal physical research data will be collected.

How will such physical research data be secured?

Data will be accessed, used, disclosed, and/or extracted and kept in a locked cabinet in or adjacent to investigator offices at Texas Children's Hospital and Baylor College of Medicine. The records will be located in personnel-restricted floors and accessible only to research personnel.

At what institution will the electronic research data be kept?

Electronic research data will be maintained by secure, institutional server or using a secured, cloud-based services at all times. Research personnel will store all research-related data in a secure manner.

Such electronic research data will be secured via BCM IT Services- provided secured network storage of electronic research data (Non-Portable devices only):

Yes

Such electronic research data will be secured via Other:

No

Will there be anyone besides the PI, the study staff, the IRB and the sponsor, who will have access to identifiable research data?

No

Please describe the methods of transmission of any research data (including PHI, sensitive, and non-sensitive data) to sponsors and/or collaborators.

N/A

Will you obtain a Certificate of Confidentiality for this study?

No

Please further discuss any potential confidentiality issues related to this study.

N/A

Section L: Cost/Payment

Delineate clinical procedures from research procedures. Will subject's insurance (or subject) be responsible for research related costs? If so state for which items subject's insurance (or subject) will be responsible (surgery, device, drugs, etc). If appropriate, discuss the availability of financial counseling.

The cost of the device and any service that is strictly research related (i.e. stent insertion, removal, study questionnaires) and outside of the normal standard of care for post-surgical or post radiation treatment will be covered by the research study. However, any clinic fees, procedures, or labs done as part of standard of care (i.e. as part of normal, post-surgical or post-treatment clinical follow-up) will not be covered by the research study. Services provided as part of standard of care will be billed to the subject's insurance.

All direct costs associated with the healthy volunteers participation will be covered by the study.

Services outside of standard of care for each patient participant group include the following:

1. Adolescent patients: - pre-operative urine analysis and vaginal culture in operating room - at 2 weeks postoperative evaluation: vaginal culture in operating room at stent removal

2. Radiation patients: - Prior to stent placement: physician vaginal assessment exam, vaginal culture, urine analysis, pregnancy test, vaginal length measurement - Evaluation at 2 weeks post stent placement: physician vaginal examination, vaginal length measurement, vaginal culture

If subjects will be paid (money, gift certificates, coupons, etc.) to participate in this research project, please note the total dollar amount (or dollar value amount) and distribution plan (one payment, pro-rated payment, paid upon completion, etc) of the payment.

Dollar Amount:

600

Distribution Plan:

Healthy participants will be compensated fairly for their time and parking. Healthy participants will be compensated \$250 for the first phase of the study (5 clinic visits, including orientation, vaginal exam/labs, insertion/removal of 2 separate stents which will be worn for 24 hrs each, questionnaires), and \$350 for the second phase of the study (3 clinic visits, vaginal exam/labs, and wearing 1 stent for 2 weeks, daily questionnaires). They will incur no cost to themselves or their insurance for participation. Vaginal exams, device, and lab fees will be paid for by the research study.

Healthy participants will be issued a ClinCard Prepaid Mastercard at the time of consent. Compensation amounts will be distributed electronically to the participant's ClinCard number upon completing clinic visits and/or surveys. The participant will be notified via email or text when the card is reloaded with additional funds.

Patient participants will not receive monetary compensation.

Section M: Genetics

How would you classify your genetic study?

Discuss the potential for psychological, social, and/or physical harm subsequent to participation in this research. Please discuss, considering the following areas: risks to privacy, confidentiality, insurability, employability, immigration status, paternity status, educational opportunities, or social stigma.

Will subjects be offered any type of genetic education or counseling, and if so, who will provide the education or counseling and under what conditions will it be provided? If there is the possibility that a family's pedigree will be presented or published, please describe how you will protect family member's confidentiality?

Section N: Sample Collection

SAMPLE: Urine

What is the purpose of the sample collection?

To determine pre-stent infection and pregnancy. This is standard of care for pre-operative adolescent patients.

For blood draws, specify the amount drawn, in teaspoons, at each visit and across the course of the subjects entire participation time.

Is there the possibility that cell lines will be developed with this sample? No

Sample will be obtained from:

Pathology

Will the sample be stripped of identifiers?

No

If sample will be released outside the hospital:

Will sample be released to anyone not listed as an investigator on the protocol? Will the information be identifiable, coded or de-identified?

no

